## 7 STATISTICAL CONSIDERATIONS

The planned statistical analyses for this study are outlined below. A detailed statistical analysis plan will be created and finalized prior to database lock and preparation of any unblinded preliminary data review and for preparation of the final study report (see Section 8).

### 7.1 Subject Populations

The safety population will consist of all randomized subjects who received at least one dose of a study drug.

The per-protocol population for efficacy or pharmacodynamic analyses will consist of all randomized subjects who received all scheduled doses of study drug and remained on study for at least 28 days. The intent-to-treat population for efficacy analyses will consist of all randomized subjects who received at least one dose of study drug.

## 7.2 Demographics and Protocol Compliance

Demographic parameters (age, sex, and race) and other baseline characteristics will be summarized by treatment group for all subjects in the safety population. Detailed demographic descriptions will be provided in the statistical analysis plan (SAP).

Listings of randomized subjects who missed any dose of study drug and of subjects with protocol deviations (to be defined in the statistical analysis plan) will be provided.

## 7.3 Efficacy or Pharmacodynamic (Serum Rabies Virus Neutralizing Activity) Analyses

Analysis of Pharmacodynamics

### Criteria for Pharmacodynamic Similarity Acceptance

Rabies Virus Neutralizing Activity plotted against time will be created. Pharmacodynamic parameters for SYN023 mAb will be estimated using non-compartmental analysis. Cmax, Tmax, AUC0-last, AUC0-inf will be calculated. For the comparison of RIG to SYN023 with RVi and RVa vaccines: The 90% confidence intervals for the ratio of geometric means (RIG/SYN023) must be 80% to 125%. An ANOVA of the ln-transformed AUC0-inf will be run to determine the 90% confidence interval on the difference between treatments. The confidence interval limits derived on the log scale will be back-transformed to the raw AUC scale for comparison to the acceptance criteria.

To investigate any interference of SYN023 to the immune response generated by the vaccine, a non-inferiority test of the AUC14-last between RIG and SYN023 for each vaccine can be performed. The one-sided 90% confidence interval derived on the log transformed AUC from an ANOVA would be compared to the lower acceptance criterion of 80%.

Additionally, a non-inferiority test of the level of RVNA between RIG and SYN023 for each vaccine at selected time points, such as 14 or 28 days, can be performed using a Wilcoxon rank sum approach with a non-inferiority of 10% of the level associated with RIG. Pharmacodynamic efficacy will be defined as RVNA measured above 0.5 IU/mL with RVi and RVa for the duration of the trial and no more than 10% lower for SYN023 compared to RIG at any time point through Study Day 35.

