### RATIONALE:

The lowest dose of SYN023 tested in Protocol SYN023-001(0.3 mg/kg) exceeded rabies virus neutralizing activity ( $\geq 0.5$  IU/mL) in the serum for at least 35 days. The two higher doses of 1.0 mg/kg and 3.0 mg/kg exceeded rabies virus neutralizing activity for 84 days. This means that the lowest dose of SYN023 administered to humans will likely produce a bridge of rabies neutralizing activity until the rabies neutralizing response to vaccination becomes therapeutic, usually in two to three weeks after vaccination. Since high levels of antibody have the potential to impair the immune response to the rabies vaccine it is important to evaluate the potential of 0.3 mg/kg SYN023 to inhibit the immune response of the two licensed rabies vaccines Imovax® and Rabavert®.

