The passive administration of RIG is intended to provide an immediate supply of virus neutralizing antibodies to bridge the gap until the induction of active immunity in response to vaccine administration. The use of RIG provides rapid passive immunity that persists for a short time (half-life of approximately 21 days) (Manning et al. 2008). There is sometimes an interaction between RIG and the immune response elicited by the rabies vaccine thus the dose of rabies immune globulin must be evaluated to insure no significant inhibition (Vodopija 1988b).

Two anti-rabies immunoglobulin (Ig) formulations prepared from hyperimmunized human donors have been approved by the FDA: HyperRab® S/D (Grifols Therapeutics) and Imogam®

Rabies-HT (Sanofi Pasteur). Since both human RIG preparations are considered equivalent HyperRab® S/D will be used as the RIG in this trial.

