3.1 General Design

This is a Phase 2 single site, randomized, blinded comparison of the immunogenicity of RVi and RVa when administered with RIG or SYN023. Up to 160 subjects are planned to be included in this study. Subjects will be randomized into one of four treatments with a ratio of 1:1:1:1 (40 subjects per treatment). All injections will be given intramuscularly.

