10.4.1 Similarity Acceptance

Using GLM procedures in SAS[®], ANOVA will be performed on untransformed $T_{\max,E}$ and ln-transformed $AUEC_{0-t}$, $AUEC_{0-7}$, $AUEC_{0-14}$, $AUEC_{14-t}$, $AUEC_{14-35}$, and E_{\max} at the alpha level of 0.05. Factors incorporated in the model will include: Vaccine, IG, and Vaccine*IG. Vaccine, IG, and Vaccine*IG will be tested against the residual mean square error. In the case of a non-statistically significant Vaccine*IG interaction term, the analysis will be rerun excluding this term from the ANOVA model in order to obtain ratios and confidence intervals where appropriate. In the case of statistically significant Vaccine*IG interaction term, the analysis will be rerun for each vaccine separately. All sums of squares (Types I, II, III and IV) will be reported. Probability (p) values will be derived from Type III sums of squares. Coefficients of variation (CV%) will be estimated.

Based on pairwise comparisons of the ln-transformed $AUEC_{0-t}$, $AUEC_{14-t}$, and E_{\max} data, the ratio (RIG/SYN023) of the geometric least-squares means, calculated according to the formula “ $e^{(X-Y)} * 100$ ”, as well as the corresponding 90% geometric confidence intervals will be determined.

For $AUEC_{14-t}$, a statistically significant Vaccine*Conmed interaction term will be interpreted as a possible interference of RIG or SYN023 on the vaccines. In this case, each vaccine will be investigated separately.

Additional analyses may be performed.

Criteria for Similarity

Considering PP population, the 90% geometric confidence intervals of the ratio (RIG/SYN023) of least-squares means from the ANOVA of the ln-transformed $AUEC_{0-t}$ must be within 80.00% to 125.00%.

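### The AUC14-last comparison in protocol 7.3 can show only interference of SYN023 beyond that of RIG, not any interference with the vaccine response

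*Protocol*

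**What the plan says.** The Rationale in the Study Abstract says that "it is important to evaluate the potential of 0.3 mg/kg SYN023 to inhibit the immune response of the two licensed rabies vaccines"; protocol 1.5 repeats this aim. Protocol 7.3 (Criteria for Pharmacodynamic Similarity Acceptance) turns it into a test whose purpose is "To investigate any interference of SYN023 to the immune response generated by the vaccine". The same sentence names the contrast: AUC14-last "between RIG and SYN023 for each vaccine can be performed". The result is judged by a one-sided 90% confidence interval against a lower limit of 80%.

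Protocol Table 2.2-1 and SAP 3.1 and 3.3 define four arms of 40: each vaccine with RIG and each vaccine with SYN023. There is no vaccine-only arm, and neither document supplies an external vaccine-only reference.

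On RIG, protocol 1.1 says "There is sometimes an interaction between RIG and the immune response elicited by the rabies vaccine" and that its dose "must be evaluated to insure no significant inhibition".

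The SAP renames the parameter AUEC14-t (SAP 4). In 10.4.1 it reports the RIG/SYN023 ratio with a 90% interval but sets no acceptance limit for it. It adds that a significant vaccine-by-antibody interaction on AUEC14-t (written there as Vaccine × Conmed) "will be interpreted as a possible interference of RIG or SYN023 on the vaccines".

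**The concern.** The stated aim is absolute: does SYN023 inhibit the response to the vaccine? The contrast is relative: is the response with SYN023 lower than with RIG? The two coincide only if RIG itself does not inhibit, and the protocol says that it sometimes interacts. If both antibodies reduce the vaccine response by the same factor, the factor cancels in the ratio and the test passes as readily as if neither inhibited.

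This is separate from passive antibody adding to measured RVNA; it would remain if RVNA were entirely vaccine-induced. What is at stake is the conclusion that a pass can carry. The SAP sentence has a related problem: it treats as the sign of interference a term that need not respond to interference at all.

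**Working it through.** **The plan's own figures.** The protocol gives no figure for interference against vaccine alone. Its sizing figures in 7.7 reproduce, but they concern SYN023 against RIG. With margin 2, SD 3, true difference 0, one-sided 5% and 80% power, a two-sample t calculation gives 29 per group. With 40 per group, SD 3, difference 2 and one-sided 2.5%, power is 0.8376 (stated: 0.838).

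**What the ratio measures.** Let i_S and i_R be the proportional inhibition of the vaccine response by SYN023 and by RIG. I take the 80% limit to apply to SYN023/RIG, the direction in which a shortfall with SYN023 lowers the ratio. If the AUC were purely vaccine-induced, the expected ratio would be

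(1 − i_S) / (1 − i_R).

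- Equal inhibition of 30%: 0.70/0.70 = 1.00. Equal inhibition of 50%: 0.50/0.50 = 1.00.
- RIG 0%, SYN023 30%: 0.70/1.00 = 0.70.
- RIG 30%, SYN023 40%: 0.60/0.70 = 0.857.

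**Chance of passing.** Noncentral t on the log scale, 40 per arm, limit 0.80, one-sided 10%, SD = √ln(1 + CV²). Protocol 7.7 assumes CVs of 10–20% for AUC and 15–25% for RVNA level; 40% is my assumption.

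| RIG / SYN023 inhibition | Ratio | CV 15% | CV 25% | CV 40% |
|---|---|---|---|---|
| 0% / 0% | 1.00 | 1.00 | 0.997 | 0.90 |
| 30% / 30% | 1.00 | 1.00 | 0.997 | 0.90 |
| 50% / 50% | 1.00 | 1.00 | 0.997 | 0.90 |
| 30% / 40% | 0.857 | 0.78 | 0.49 | 0.31 |
| 0% / 30% | 0.70 | <0.001 | <0.001 | 0.002 |

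Common inhibition leaves the chance of passing unchanged. Excess inhibition is visible.

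**Translation to vaccine alone.** At ratio m, inhibition by SYN023 against vaccine alone is 1 − (1 − r) × m, where r is RIG's own inhibition. The documents do not give r, so a range is assumed. With m = 0.80:

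- r = 0: 1 − 1.00 × 0.80 = 20%
- r = 10%: 1 − 0.90 × 0.80 = 28%
- r = 20%: 1 − 0.80 × 0.80 = 36%
- r = 30%: 1 − 0.70 × 0.80 = 44%

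**The interaction term in SAP 10.4.1.** On the log scale it is the log SYN023/RIG ratio for one vaccine minus that for the other. If each antibody inhibits both vaccines by the same factor, it is zero. For example, RIG 0% and SYN023 30% with both vaccines gives ln 0.70 − ln 0.70 = 0, although SYN023 is 30% below RIG. The term shows only whether the ratio differs between vaccines.

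**The 0.5 IU/mL criterion.** This does not depend on RIG. In protocol Table 1.5-1, 0.3 mg/kg SYN023 without vaccine gave mean RVNA of 3.78, 2.82 and 1.82 IU/mL on Days 14, 28 and 35, so passive antibody alone meets the criterion on average at those visits. By Day 84 the mean was 0.22 IU/mL, so values above 0.5 at Days 84 and 112 should be largely vaccine-induced. The check is coarse: a vaccine-induced level cut by 30% still exceeds 0.5 whenever it would otherwise have exceeded 0.5/0.70 = 0.71 IU/mL.

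**The case against.** The comparator is not hidden: purpose and contrast stand in one sentence of 7.3, so the purpose can be read as interference relative to the comparator named there. Vaccine plus RIG is the standard of care (protocol 1.1), and the primary objective is a comparison with RIG. All of this stands, and it is why the comparison itself needs no change. It does not remove the difference between the absolute aim and the relative test, because the Rationale states the aim without reference to RIG.

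A reader might infer that a pass will be reported as absence of interference. Neither document says so: the protocol test is optional, and the SAP's only similarity criterion is for AUEC0-t. The point concerns what the wording invites, not a conclusion already planned.

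The conversion to 28%, 36% or 44% is also open to challenge. Protocol 1.1 says only that RIG sometimes interacts, and reports no inhibition at the study dose. The endpoint is total RVNA, which includes passive antibody after Day 14, and the SAP uses the area above 0.5 IU/mL, which breaks strict proportionality. These figures illustrate the logic; they do not estimate an effect on the planned endpoint.

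Protocol 1.1 also cites a finding of no RVNA inhibition when RIG followed vaccine by up to 4 days. That does not settle the matter here, because vaccine is given within 75 minutes after the antibody.

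**Conclusion.** The point holds as a limit on the claim. The AUC14-last comparison can show interference of SYN023 beyond that of RIG; it cannot show whether SYN023 interferes at all. Exact cancellation assumes equal proportional inhibition and a vaccine-induced AUC, and the size of any masked inhibition depends on r, which the documents do not give.

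Three stronger readings are not supported:

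- *Interference cannot be assessed.* Excess over RIG can be, as the ratio of 0.70 above shows.
- *The design is invalid or needs a vaccine-only arm.* The primary objective is a comparison with RIG, and the four arms deliver it.
- *Nothing in the trial is independent of RIG.* RVNA above 0.5 IU/mL at Days 84 and 112 would reveal gross loss of response, though not partial inhibition. The Day 84 passive level behind this is a mean of five Phase 1 subjects.

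**What to change.** **Protocol 7.3 and the matching rationale wording (Study Abstract and 1.5).** Describe the aim as *interference of SYN023 beyond that of RIG*. State that there is no vaccine-only arm. State that a pass supports only the conclusion that the response with SYN023 is not more than the margin below that with RIG, and does not show absence of interference.

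**SAP 10.4.1.** Do not insert the same phrase, because the sentence there concerns an interaction. State instead that:

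- a significant vaccine-by-antibody interaction on AUEC14-t shows only that the RIG/SYN023 ratio differs between vaccines;
- a non-significant interaction is not evidence of no interference;
- interference relative to RIG is judged from the AUEC14-t ratio and its confidence interval.

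**Cost.** Wording in two documents; no change to subjects, samples or analyses. The downside is a narrower and less favourable claim.

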10.3 Efficacy/Pharmacodynamic Parameters

A total of 10 blood samples will be drawn from each subject for efficacy/PD analyses. Blood samples will be collected on Day 0, Day 1, Day 3, Day 7, Day 14, Day 28, Day 35, Day 42, Day 84, and Day 112.

RVNA will be used to calculate the following parameters by standard non-compartmental methods:

AUEC_{0-t}: area under the effect-time curve above the minimum rabies virus neutralizing activity threshold (0.5 IU/mL) from time 0 to the last measurable concentration, calculated using the linear trapezoidal method. Unit will be Day*IU/mL.

AUEC₀₋₇: area under the effect-time curve above the minimum rabies virus neutralizing activity threshold (0.5 IU/mL) from time 0 to 7 days, calculated using the linear trapezoidal method. In case where the 7 days RVNA value is missing, AUEC₀₋₇ will be interpolated at the discretion of the pharmacokineticist. Unit will be Day*IU/mL.

- AUEC₀₋₁₄: area under the effect-time curve above the minimum rabies virus neutralizing activity threshold (0.5 IU/mL) from time 0 to 14 days, calculated using the linear trapezoidal method. In case where the 14 days RVNA value is missing, AUEC₀₋₁₄ will be interpolated at the discretion of the pharmacokineticist. Unit will be Day*IU/mL.
- AUEC_{14-t}: area under the effect-time curve above the minimum rabies virus neutralizing activity threshold (0.5 IU/mL) from time 14 days to the last measurable concentration, calculated using the linear trapezoidal method. In case where the 14 days RVNA value is missing, AUEC_{14-t} will be interpolated at the discretion of the pharmacokineticist. Unit will be Day*IU/mL.
- AUEC₁₄₋₃₅: area under the effect-time curve above the minimum rabies virus neutralizing activity threshold (0.5 IU/mL) from time 14 days to 35 days, calculated using the linear trapezoidal method. In case where the 14 days or 35 days RVNA value is missing, AUEC₁₄₋₃₅ will be interpolated at the discretion of the pharmacokineticist. Unit will be Day*IU/mL.
- E_{max}: maximum observed effect. Unit will be IU/mL.
- T_{max,E}: time of observed E_{max}. Unit will be Day.

Some efficacy/PD parameters may not be calculated for all or some subjects, at the discretion of the inVentiv pharmacokineticist, if the concentration data is not deemed to be amenable to evaluation. Explanations for efficacy/PD parameters that could not be estimated will be provided in the CSR.

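### The protocol's test for SYN023 interference from Day 14 onward allows a one-sided 10% error, and the SAP keeps an interval for it but no pass rule

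*Protocol*

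**What the plan says.** **Protocol 7.3.** For the main comparison, "The 90% confidence intervals for the ratio of geometric means (RIG/SYN023) must be 80% to 125" percent. For interference, a non-inferiority test of AUC14-last "between RIG and SYN023 for each vaccine can be performed", and "The one-sided 90% confidence interval derived on the log transformed AUC from an ANOVA would be compared to the lower acceptance criterion of 80" percent. The wording makes this test optional.

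**SAP section 4** replaces AUC14-last with AUEC14-t and presents the switch as a matter of nomenclature. SAP 10.3 defines the new parameter as the "area under the effect-time curve above the minimum rabies virus neutralizing activity threshold (0.5 IU/mL) from time 14 days to the last measurable concentration".

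**SAP 10.4.1** reports the RIG/SYN023 ratio for AUEC0-t, AUEC14-t and Emax, "as well as the corresponding 90% geometric confidence intervals will be determined". The only acceptance criterion is for AUEC0-t, whose interval "must be within 80.00% to 125.00" percent. For AUEC14-t, a significant interaction (written Vaccine*IG in one place and Vaccine*Conmed in another) "will be interpreted as a possible interference of RIG or SYN023 on the vaccines", and each vaccine is then examined separately. If the interaction is not significant, "the analysis will be rerun excluding this term from the ANOVA model in order to obtain ratios and confidence intervals where appropriate", so the two vaccines are pooled.

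**The concern.** The protocol's rationale is to find out whether 0.3 mg/kg SYN023 inhibits the response to the two licensed vaccines. The area from Day 14 onward is the analysis that Protocol 7.3 assigns to that question, yet it carries twice the per-side error of the overall similarity claim, with no reason given.

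The SAP then produces an interval for this parameter without saying how to read it. After unblinding, an analyst could read it at 5% or 10%, pooled or per vaccine, against the lower or the upper limit, or could report only the interaction. A conclusion of no interference would rest on a choice made after the data were seen.

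**Working it through.** **Inputs.** 40 subjects per arm (Protocol 2.2). Limit 80% (Protocol 7.3). AUC power statement: bound 0.9, 40 per group, CV 10-20%, power over 80%, no alpha given (Protocol 7.7). Assumed here: the SAP's 90% intervals are two-sided, the true ratio is 1 where power is quoted, and CVs above 20% are illustrative.

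**Formulas.** Log scale, parallel groups, n = 40 v 40, df = 78:
- SD = sqrt(ln(1 + CV²)); SE = SD × sqrt(2/40)
- Power from the noncentral t, with noncentrality ln(true ratio / bound) / SE
- Smallest passing SYN023/RIG ratio = 0.80 × exp(t × SE), with t = 1.293 (one-sided 10%) or 1.665 (one-sided 5%)

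**1. The plan's own AUC power.** At CV 20%, SD = sqrt(ln 1.04) = 0.1980 and SE = 0.1980 × 0.2236 = 0.0443. The noncentrality is ln(1/0.9)/0.0443 = 2.38.

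| One-sided alpha | CV 10% | CV 15% | CV 20% |
|---|---|---|---|
| 0.10 | 100% | 96.9% | 86.1% |
| 0.05 | 99.9% | 93.1% | 76.2% |
| 0.025 | 99.7% | 87.7% | 65.2% |

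Per vaccine, power over 80% across the whole CV range reproduces only at one-sided 10%. Pooled at 80 v 80, it holds at every level (CV 20%: 98.1%, 95.6% and 91.7%). The unstated alpha therefore decides whether the per-vaccine claim is true.

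**2. Error rates.** A one-sided 90% interval gives alpha = 1 − 0.90 = 0.10. A two-sided 90% interval gives (1 − 0.90)/2 = 0.05 per side.

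**3. Effect on the threshold, if the 80% limit is applied per vaccine.** At CV 20%: 0.80 × exp(1.293 × 0.0443) = 0.847 and 0.80 × exp(1.665 × 0.0443) = 0.861.

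| CV | Passes at 10% error from | Passes at 5% error from |
|---|---|---|
| 10% | 0.823 | 0.830 |
| 20% | 0.847 | 0.861 |
| 30% (assumed) | 0.871 | 0.892 |
| 50% (assumed) | 0.917 | 0.954 |

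At CV 20% the two levels would disagree in about 14.5% of trials if the true ratio were 0.85, and in 7.4% if it were 0.90.

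**4. What the interaction test can see.** Let r_i and r_a be the true SYN023/RIG ratios of geometric means with RVi and RVa. On the log scale the interaction is ln r_i − ln r_a. If SYN023 suppresses both responses equally, r_i = r_a and the interaction is exactly zero, however small the common ratio. The 5% test then fires in only 5% of trials, the same as with no suppression, and a non-significant result leads to pooling.

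**5. Direction.** The ratio defined in both documents is RIG/SYN023. A weaker response with SYN023 raises it, so the limit that guards against interference is the upper one: 1/0.80 = 125%. The protocol's lower limit of 80% guards against interference only if the ratio is SYN023/RIG, and the interference paragraph does not state a direction.

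**The case against.** The protocol test is optional and secondary: SAP section 5 makes AUEC0-t the primary parameter. Protocol 7.8.2 allows the SAP to modify the protocol's analyses, so the SAP governs. A one-sided 10% level is written explicitly, may be deliberate for a supportive Phase 2 check, and need not match the similarity criterion. At the protocol's own CVs the two thresholds differ by only 0.007 to 0.014.

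Most of this stands. It limits the size of the point, and it shows that matching the two levels is a recommendation rather than something the documents require. It does not account for the SAP's silence. Section 4 exists to record changes, and it lists neither the dropped non-inferiority rule nor the interaction rule that takes its place.

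A reader might go further and infer that a borderline result would pass one document and fail the other. The documents do not support that. The SAP sets no limit for AUEC14-t, so nothing can fail there. It also pools the vaccines by default and measures area above 0.5 IU/mL, so neither the comparison nor the parameter is strictly the same. The per-vaccine thresholds above show what the choice of level does once a limit is adopted; they do not describe the SAP's default analysis.

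Nor is equal suppression invisible in the SAP's output. The RIG/SYN023 ratio and its interval would show it, but no rule tells the analyst to act on them.

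**Conclusion.** The concern holds in a limited form. The interference test in Protocol 7.3 is set at a one-sided 10% error, laxer than the 5% per side used for similarity. The SAP carries forward an interval (5% per side if two-sided) without a limit, and its one stated interference rule cannot detect suppression common to both vaccines. SAP section 4 lists neither change.

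The level alone has a modest effect: 0.007 on the passing ratio at CV 10% and 0.014 at CV 20%, more only at assumed larger CVs. The missing rule matters more, because without it the planned analysis cannot support a prespecified conclusion on interference. This should be corrected before database lock, the point by which Protocol section 7 says the SAP will be final.

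**What to change.** - **Protocol 7.3:** replace the one-sided 90% confidence interval with a two-sided 90% confidence interval (one-sided 95% bound), and state the ratio direction.
- **SAP 10.4.1:** add that interference is judged on AUEC14-t for each vaccine separately. The lower limit of the two-sided 90% interval for SYN023/RIG must be at least 80% (equivalently, the upper limit for RIG/SYN023 at most 125%). The interaction test is supportive.
- **SAP section 4:** list this as a change, and note that AUEC14-t is area above 0.5 IU/mL rather than a renamed AUC14-last.
- **Protocol 7.7:** state the alpha behind the AUC power claim, and reconcile its 0.9 bound with the 80% limit in 7.3.

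**Cost.** A few sentences and no new data. The SAP already specifies the pooled interval and, when the interaction is significant, the per-vaccine rerun; the rerun would become unconditional. At the 80% limit and a true ratio of 1, per-vaccine power stays above 99.9% at CV 20%. It falls from 98.2% to 95.8% at an assumed CV of 30%, and from 79.4% to 67.3% at an assumed CV of 50%. If the 0.9 bound is kept in 7.7, the per-vaccine power claim at CV 20% must be restated as 76.2%.
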